3.3 Part A: Dose-Escalation and Determination of MTD

The Dose-Escalation phase will follow a standard 3+3 cohort design. Three patients will be treated at each dose level. If 0/3 patients experience DLT, 3 patients will be treated at the next dose level. If DLT attributable to the treatment is experienced in 1/3 patients, three more patients (for a total of six patients) will be treated at that dose level. If no additional DLT is observed at the expanded dose level (i.e. 1/6 with DLT), the dose will be escalated. Escalation will terminate as soon as two or more patients experience any DLT attributable to study drugs, at a given dose

level. DLT and determination of MTD will be based on cycle 1 toxicities. Intra-patient dose escalation will not be allowed. Six patients will be treated at the MTD. The MTD cohort may be expanded by an additional 10 patients for further toxicity and response assessment. If MTD is not reached, the study team will determine the RP2D for further evaluation in Part B, cohort expansion. If ≥ 2 out of 6 DLTs occur for Dose Levels -1, 1, or 2, the dosing schedule may be amended to determine the appropriate scheduling regimen.

No. of Patients with DLT at a Given Dose Level	Escalation Decision Rule
0 out of 3	Enter patient(s) at the next dose level.
≥ 2	Dose escalation will be stopped. This dose level will be declared the maximally administered dose (highest dose administered). Three additional patients will be entered at the next lowest dose level if only 3 patients were treated previously at that dose level.
1 out of 3	
Enter at least 3 more patients at this dose level.
 
 If 0 of these 3 patients experiences DLT, proceed to the next dose level. If 1 or more of this group suffer DLT, then dose escalation is stopped and this dose is declared the maximally administered dose. Three additional patients will be entered at the next lowest dose level if only 3 patients were treated previously at that dose.
≤ 1 out of 6 at highest dose level below the maximally administered dose	This will be the MTD. At least 6 patients will be entered at this dose.

3.4 Part A Dose Escalation Schedule and Treatment Schema

Oral PCLX-001 will be provided as continuous daily dosing on a 28-day cycle. The starting dose of PCLX-001 will be 20 mg daily (Section 3.1.1). Dose escalation will follow a modified Fibonacci design such that the magnitude of escalation decreases as the dose level nears the human equivalent dose (HED) of the HNSTD in dogs and then escalate at 1.4 times the previous dose until MTD or RP2D is reached.

The dose level schedule is as below (1 cycle = 28 days):

Dose Level**	Daily Oral Dose (mg)	Number of Capsules	
		10 mg	70 mg
-1	10	1	0
1 (starting dose)*	20	2	0
2	40	4	0
3	70	0	1
4	100	3	1
5	140	0	2
6	210	0	3
7	280***	0	4

* Trial will start at Dose Level 1 and will de-escalate to Dose Level -1 if DLT is observed.

** If ≥ 2 out of 6 DLTs are observed in Dose Level -1, 1 or 2 then consideration will be given to changing dosing schedule (eg. 28-day schedule with each week comprising 4 days on medication and 3 days off medication).

*** If DLT is not observed at the dose of 280 mg, the dose will be considered the MTD. If required, the MTD cohort may be expanded by an additional 10 patients for further toxicity and response assessment.

For each dose-escalation cohort, treatment with the first dose of PCLX-001 will be staggered such that the second participant enrolled in the cohort will receive PCLX-001 at least two weeks after the first participant and all subsequent participants at least one week after the previous participant.

Each participant will be treated with the dose of PCLX-001 they are assigned to, until the occurrence of a DLT or other study stopping point occurs, at which point the dose of PCLX-001 will be modified as per protocol or study drug administration will be discontinued.

If DLT occurs at Dose Level 1, a safety meeting will occur to determine the feasibility of continuing the study at Dose Level -1. Alternative dose schedules may also be considered if DLTs occur during Dose Levels, -1, 1 or 2.

Participants who experience a DLT or have received at least 21 days of PCLX-001 during cycle 1 will be evaluable for toxicity. If a participant does not meet these criteria, the participant may be replaced (Section 4.3).

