10.5 Safety Stopping Rules

Accrual will be on hold and a meeting held with the principal investigator, investigators and safety monitoring team if the following occurs:

- If there is a death or unacceptable toxicity (SAE or AE grade ≥ 3 .) attributed as: possibly, probably or definitely related to the experimental product.
- If there is a protocol treatment-related Serious Adverse Event (any SAEs deemed by PI to be definitely, probably or possibly related to study drug), or any significant safety concerns
- If the first 2 patients enrolled experience DLT

A decision will be made by the PI and safety monitoring team regarding whether the study will be re-opened for the next patient in the study or not. If there is disagreement in the SAE causality assessment or whether or not to re-open accrual between the different parties, the final decision will rest on the safety monitoring team. Ozmosis Research will notify all sites and applicable parties on the decision and whether accrual has re-opened. Only when it is deemed safe can the next patient start the treatment phase of the study.

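### Dose-decision wording conflicts at both ends of the escalation: a footnote de-escalates on any DLT at Dose Level 1 where Section 3.3 expands to six, and 280 mg has no written step to reach the six patients an MTD needs

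*Combined protocol and SAP*

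**What the plan says.** **Dose Level 1 (20 mg).** Footnote * in Section 3.4, repeated in the Synopsis, reads "Trial will start at Dose Level 1 and will de-escalate to Dose Level -1 if DLT is observed". The text of Section 3.3 says that after 1/3 "three more patients (for a total of six patients) will be treated at that dose level", and its decision table says "Enter at least 3 more patients at this dose level". Neither excepts the starting dose. Footnote **, under the same dose table, begins "If ≥ 2 out of 6 DLTs are observed in Dose Level -1, 1 or 2". The body of 3.4 adds: "If DLT occurs at Dose Level 1, a safety meeting will occur to determine the feasibility of continuing the study at Dose Level -1". Section 10.5 puts accrual on hold after serious or severe related toxicity and ends: "Only when it is deemed safe can the next patient start the treatment phase of the study".

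**Dose Level 7 (280 mg, the last level listed).** Footnote *** reads "If DLT is not observed at the dose of 280 mg, the dose will be considered the MTD". The 3.3 table row for 0/3 is "Enter patient(s) at the next dose level", and the branch for 1/3 followed by 0/3 also moves up a level. Sections 3.1, 3.2 and 3.3 all call for six patients at the MTD, and 3.2 makes six patients evaluable for toxicity part of the definition. If no MTD is reached, 3.3 lets the study team choose the RP2D.

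**Size.** Section 8.1 gives Part A as 9 to 52 patients.

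**The concern.** Determining the MTD and/or RP2D is a primary objective, and the cohort rules drive the MTD. After exactly one DLT in the first three patients at 20 mg, the safety review would hold two written instructions that send the next patients to different doses. The meeting in 3.4 mentions only Dose Level -1 and not expansion to six, and the hold in 10.5 decides whether accrual reopens, not at which dose.

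At the top, the general table gives no usable action for either non-stopping result. The one specific rule, footnote ***, omits the number of patients. A site or safety team working from the table and footnotes alone could treat 0/3 as sufficient, or find no instruction for 1/6.

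**Working it through.** **The plan's own figure.** Section 8.1 does not derive 9 to 52, so the derivation here is inferred by counting patients under 3.3.
- Maximum: 7 levels × 6, plus the optional 10 at the MTD, = 52. This matches.
- Minimum with an MTD: 3 + 3 + 3 = 9 (0/3 at Level 1, at least two DLTs at Level 2, three more at Level 1), or 3 + 6 = 9 (at least two DLTs at Level 1, six at Level -1). This matches.
- Maximum if footnote * is taken literally: a trial that climbs to the top passes Level 1 only on 0/3, so 3 + 6 × 6 + 10 = 49. This does not match.

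Under 3.3, six patients at Level 1 on the way to the top arise only through 1/3 then 0/3. The 52 therefore fits 3.3 and not footnote *. Footnote ** points the same way, because a count out of six at Level 1 presupposes expansion.

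**Dose Level 1.** The documents give no DLT rates, so p is assumed; q = 1 − p.

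| p | exactly 1/3: 3pq² | 3.3 clears 20 mg after 1/3: q³ | advance under 3.3: q³ + 3pq⁵ | advance under literal footnote *: q³ |
|---|---|---|---|---|
| 5% | 0.135 | 0.857 | 0.973 | 0.857 |
| 10% | 0.243 | 0.729 | 0.906 | 0.729 |
| 20% | 0.384 | 0.512 | 0.709 | 0.512 |

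The second column assumes that a full cohort of three is treated before anyone acts. Starts are staggered, so a literal footnote * could act at 1/1 or 1/2, and the column does not describe that case.

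Time, from the stagger in 3.4 and a 28-day cycle: a new cohort of three at 10 mg takes at least 2 + 1 + 4 = 7 weeks. Three more patients at 20 mg take at least 1 + 1 + 4 = 6 weeks. The difference is about one week.

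**280 mg, by result.**
- *0/3.* The table points up a level and none is listed. Footnote *** displaces the table and names the MTD. Section 3.2 does not allow an MTD on fewer than six evaluable patients. No sentence enters the other three: the table adds three at a lower level only after a higher dose has been stopped.
- *1/6.* The table points up a level and none is listed. Footnote *** does not apply, because a DLT was seen. The first sentence of the 3.2 definition does apply: 1/6 = 16.7%, below 33%, in six patients. The second sentence of 3.2 and the last table row assume a higher, stopped dose, which would not exist.
- *Two or more DLTs.* The table works as written.

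The 3.4 text about multiplying the dose by 1.4 would give 280 × 1.4 = 392 mg, but no such level is in the schedule and footnote *** treats 280 mg as the end.

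| p | 0/3: q³ | 1/3 then 0/3: 3pq⁵ | after 0/3, ≥2 DLTs in three more: 1 − (q³ + 3pq²) |
|---|---|---|---|
| 10% | 0.729 | 0.177 | 0.028 |
| 20% | 0.512 | 0.197 | 0.104 |
| 33.3% | 0.296 | 0.132 | 0.259 |
| 40% | 0.216 | 0.093 | 0.352 |

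Requiring three more after 0/3 lowers acceptance on that path from 0.296 to 0.296 × (1 − 0.259) = 0.219 at 33.3%, and from 0.216 to 0.216 × (1 − 0.352) = 0.140 at 40%. One-sided 95% exact upper bounds on the DLT rate are 1 − 0.05^(1/3) = 63% for 0/3 and 1 − 0.05^(1/6) = 39% for 0/6.

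**The case against.** The strongest reply is that the intent can be recovered. Footnote * may only name where de-escalation goes, which is useful because nobody has yet been treated at Level -1. Section 3.3 declares a standard 3+3, and any DLT at Level 1 brings a safety meeting. Under 10.5, the safety monitoring team has the final word on reopening accrual if the parties disagree. Most of this stands and keeps the point small. It does not remove the conflict, because the footnote's condition is any observed DLT and the meeting's stated subject is Level -1.

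Three stronger readings are tempting and are not supported.
- *That the plan would declare 280 mg the MTD on three patients.* This requires reading footnote *** alone. Sections 3.1, 3.2 and 3.3 all require six; only the enrolment step is unwritten. The 63% bound and the drop in acceptance describe a reading that 3.2 excludes.
- *That 1/6 at 280 mg has no rule at all.* The first sentence of 3.2 qualifies it, and 3.3 has a fallback to an RP2D chosen by the study team. The gap is in the table and footnotes. The fallback is not a complete answer, since 3.5 opens Cohort A once both the MTD and the RP2D are determined.
- *That footnote * endangers patients or costs seven weeks.* It errs toward caution, and the extra time over expansion is about one week.

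Nor do these rules fix the RP2D by themselves: 3.5 bases it on all safety, PK and efficacy data and allows it to differ from the MTD.

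**Conclusion.** The point holds as a minor inconsistency. At Dose Level 1, footnote * read literally contradicts 3.3 after 1/3, and the rest of the document favours 3.3. Following the footnote would cost little time but could hold the starting level down after a single DLT, in cases where 3.3 would still clear 20 mg 86%, 73% and 51% of the time at assumed rates of 5%, 10% and 20%. At 280 mg, footnote *** lacks the six-patient condition, the step from three to six is missing, and two table rows lead to an unlisted level. A 1/6 result through 1/3 then 0/3 would arise in 18% and 20% of trials reaching 280 mg at assumed rates of 10% and 20%.

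The probabilities depend on assumed DLT rates and full cohorts. The reading of 52 as 7 × 6 + 10 is inferred. The textual conflict depends on neither.

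**What to change.** **(a) Dose Level 1.** Change footnote * in 3.4 and the Synopsis to: *Dose Level 1 follows the Section 3.3 rule; if ≥2 patients have DLT, de-escalate to Dose Level -1.* Reword the 3.4 meeting as well, since it is triggered by any DLT and now considers only Level -1. After a single DLT it should review whether expanding Level 1 to six is safe; after two or more it should decide whether Level -1 is feasible. Keep the 10.5 hold and the safety team's freedom to stop or de-escalate. The cost is that, after one DLT, three more patients may be treated at 20 mg, as 3.3 already provides.

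**(b) 280 mg.** Add a top-level row to the 3.3 table and match footnote *** in 3.4 and the Synopsis: *At 280 mg after 0/3, enter three more patients; 280 mg is accepted as MTD (or highest dose tested) if ≤1 of 6 evaluable patients has DLT, consistent with 3.2.* The choice of label is the sponsor's; keeping MTD leaves the Cohort A opening condition unchanged.

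The cost is up to three more patients and about six weeks (1 + 1 + 4) after 0/3. They fit within 52, which allows six at 280 mg. After 0/3, the added step would reject 280 mg about 3% and 10% of the time at assumed true rates of 10% and 20%. The existing six-patient requirement already implies those patients.

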3.5 Design of Part B Expansion Cohorts

Once the MTD has been defined, preliminary activity will be further evaluated in the expansion part of the study. If clinically indicated, separate cohort(s) may be open for enrollment to evaluate a different schedule of PCLX-001 (for example a break within cycles), based on safety, PK and preliminary activity data and integrated PK/efficacy and PK/safety modelling from the dose escalation. The RP2D will be defined by the sponsor in conjunction with the investigators after reviewing the data from all parts and stages of the study, including available PK data and intensity of adverse events (AEs), and efficacy parameters, including overall response rate (ORR). The RP2D may be the MTD but not necessarily as not only safety data will be taken into account prior to its determination.

Two expansion cohorts will be opened to determine the preliminary clinical activity of PCLX-001. Part B dose expansion Cohort A will occur once the MTD and the RP2D are determined by the sponsor and investigators after data review.

Part B dose expansion cohort B will occur once dose escalation has achieved a dose that has both acceptable safety and achieves drug exposures predicted to have activity in R/R B-cell lymphomas. See Appendix D for the background, rationale, and determinants of the decision to open dose expansion cohort B.

- Expansion Cohort A: 20 participants with advanced solid malignancies showing preclinical sensitivity or molecular markers of sensitivity to PCLX-001: breast, non-small cell lung, small-cell lung, colorectal, and bladder cancers
- Expansion Cohort B: 20 participants with relapsed/refractory (R/R) B-cell lymphoma: diffuse large B-cell lymphoma (including transformed disease), high grade B-cell lymphoma, follicular lymphoma, mantle cell lymphoma, and Burkitt lymphoma.

3.6 Treatment Duration and Discontinuation

In the absence of treatment delays due to adverse events, treatment may continue unless the following reasons to discontinue PCLX-001 occur:

- Disease progression
- Intercurrent illness preventing further administration of treatment
- Unacceptable adverse event(s)
- Patient withdrawal from study (patient choice)
- Treating physician choice
- Delay in subsequent cycles of chemotherapy of longer than 28 days due to toxicity
- Failure of patient to adhere to study requirements

3.7 End of Treatment and Follow-Up

All patients (except for patients who died, withdrew consent and objected to further data collection, or were lost to follow-up) will be followed for 30 days (\pm 4 days) after the last dose of study drug or until all treatment related clinically significant adverse events resolve to Grade \leq 1. Patients will have their medical records evaluated every 6 months (\pm 1 month) for a period starting three years from enrollment, to determine survival status (alive, deceased, and date of death).

4. STUDY POPULATION

Patients with histologically confirmed solid tumors or B-cell lymphoma resistant or refractory to standard therapy or without standard therapy and in which, in the opinion of the investigator, experimental treatment with PCLX-001 may be of benefit will be recruited.

Patients must have baseline evaluations performed prior to the first dose of study drug and meet all eligibility criteria. Results of all baseline evaluations, which assure that all inclusion and exclusion criteria have been satisfied, must be reviewed by the Principal Investigator or his/her designee prior to enrollment of the patient. The patient must be thoroughly informed about the aspects of the study, including the study visit schedule and required evaluations and all regulatory requirements for informed consent. The written informed consent must be obtained from the patient prior to enrollment.

4.1 Inclusion Criteria

Patient must meet all of the following criteria to be eligible for the study.

The following inclusion criteria apply to ALL (dose-escalation and expansion) patients:

1. Ability to understand and the willingness to sign a written informed consent. A signed informed consent must be obtained before any study-specific procedures are performed.
2. Male or female patients aged \geq 18 years
3. **Dose Escalation**
 - a. Participants with histologically-confirmed advanced solid tumor (non-breast cancer) who have failed at least one prior therapy and/or are not eligible for therapies expected to provide clinical benefit.
 - b. Participants with histologically-confirmed metastatic breast cancer with known hormone receptor status meeting the therapy requirements as listed below (just prior to criterion #4).
 - c. Histologically-confirmed B-cell lymphomas that are expected to express CD20 including DLBCL, HGBL, FL (grades 1 to 3b), MCL, and Burkitt lymphoma who have failed at least two prior therapies and/or are not eligible for therapies expected to provide clinical benefit (including autologous stem cell transplantation). Transformed large B-cell lymphoma patients are eligible. FL patients should meet criteria for requiring treatment. These histologic subtypes are based on WHO 2016 criteria.

Dose Expansion

Cohort A: Participants with histologically-confirmed advanced NSCLC, SCLC, colorectal, and bladder cancers who have failed at least one prior therapy and/or are not eligible for therapies expected to provide clinical benefit. Participants with histologically-confirmed metastatic breast cancer with known hormone receptor status meeting the therapy requirements as listed below (just prior to criterion #4).

Cohort B: Participants with histologically-confirmed R/R B-cell lymphomas that are expected to express CD20 including DLBCL, HGBL, FL (grades 1-3a), FL (grade 3b), MCL, and

Burkitt lymphoma who have failed at least two prior therapies and/or are not eligible for therapies expected to provide clinical benefit. Transformed large B-cell lymphoma patients are eligible. FL patients should meet criteria for requiring treatment.

Therapy requirements and stratification factors for histologically-confirmed metastatic breast cancer participants in either the dose escalation or dose expansion phases are dependent upon hormone receptor status as follows:

i. **Estrogen Receptor positive and/ or Progesterone Receptor positive, and HER 2 negative disease.**

Prior treatment with:

- Two or more lines of endocrine therapy in the adjuvant or metastatic setting including the following: Selective Estrogen Receptor Modulators (eg. tamoxifen), Aromatase Inhibitors (eg. letrozole, anastrozole, exemestane), Selective Estrogen Receptor Downregulators (fulvestrant), and CDK4/6 inhibitors (palbociclib, ribociclib, abemaciclib) in combination or monotherapy, and
- at least three lines of cytotoxic chemotherapy given in the adjuvant, neoadjuvant, or metastatic setting including an anthracycline, a taxane, and capecitabine.

ii. **Estrogen Receptor and Progesterone Receptor and HER2 negative disease.**

- Prior treatment with at least three lines of cytotoxic chemotherapy in the adjuvant or metastatic setting including the following agents: anthracyclines, taxanes, platinum (carboplatin or cisplatin), and
- if known BRCA1 or BRCA2 mutated disease, prior PARP inhibitor therapy is required if available to the patient.

iii. **HER2 positive disease with negative Estrogen receptors.**

- Prior treatment with three or more lines of HER2-directed therapy in the adjuvant, neoadjuvant, or metastatic setting including at least three of the following HER2 directed agents: trastuzumab, trastuzumab emtansine, trastuzumab deruxtecan, pertuzumab, lapatinib, neratinib, tucatinib.

iv. **HER2 positive disease with positive Estrogen receptors.**

Prior treatment with:

- three or more lines of HER2-directed therapy in the adjuvant, neoadjuvant, or metastatic setting including at least three of the following HER2 directed agents: trastuzumab, trastuzumab emtansine, trastuzumab deruxtecan, pertuzumab, lapatinib, neratinib, tucatinib, and
- two or more lines of endocrine therapy in the adjuvant or metastatic setting including the following: Selective Estrogen Receptor Modulators (eg. tamoxifen), Aromatase Inhibitors (eg. letrozole, anastrozole, exemestane), Selective Estrogen Receptor Downregulators (fulvestrant), and CDK4/6 inhibitors (palbociclib, ribociclib, abemaciclib) in combination or monotherapy, and
- at least three lines of cytotoxic chemotherapy given in the adjuvant, neoadjuvant, or metastatic setting including an anthracycline, a taxane, and capecitabine.

4. Patients must have evaluable or measurable disease (as per Response Evaluation Criteria in Solid Tumors, version 1.1 [RECIST 1.1], or the Lugano lymphoma classification).
5. Eastern Cooperative Oncology Group (ECOG) performance status of 0 to 1 (Appendix A).
6. Life expectancy of at least 12 weeks

7. Patients must have adequate bone marrow function as assessed by the following laboratory tests to be conducted within 7 (± 3) days before the first dose of study drug:
 - a. Hemoglobin ≥ 85 g/L
 - b. Absolute neutrophil count (ANC) $\geq 1.5 \times 10^9$ /L
 - c. Platelet count $\geq 100 \times 10^9$ /L for Dose Escalation and $\geq 75 \times 10^9$ /L for Dose Expansion

NOTE: For Dose Expansion, patient who do not meet the above hematological criteria, because of bone marrow suppression from prior therapies and/or extensive tumour involvement in the marrow, may be considered for enrollment in the trial after consultation with the Medical Monitor.

8. Patients must have adequate kidney function, as assessed by both: a) the estimated glomerular filtration rate (eGFR) ≥ 50 mL/min within 7 (± 3) days before the first dose of study drug (eGFR to be calculated by the Cockcroft-Gault formula), and b) creatinine ≤ 1.5 times the ULN
9. Patients must have adequate coagulation, as assessed by the following laboratory tests to be conducted within 7 (± 3) days before the first dose of study drug:
 - a. Prothrombin time/International normalized ratio (PT/INR) ≤ 1.5 for patients not on anticoagulation
 - b. Activated partial thromboplastin time (aPTT) ≤ 1.5 times ULN for patients not on anticoagulation

Note: Patients on anticoagulation with an agent such as heparin (eg. enoxaparin, dalteparin, etc.) will be allowed to participate if no prior evidence of underlying abnormality in coagulation parameters exists.

10. Adequate cardiac function per institutional normal measured by echocardiography or multigated acquisition (MUGA) scan (LVEF $\geq 50\%$)
11. Women of childbearing potential must have a negative serum beta human chorionic gonadotropin (β -HCG) pregnancy test obtained within 7 (± 3) days before the start of administration of study drug.

Note: A woman is of childbearing potential, i.e. fertile, following menarche and until becoming postmenopausal unless permanently sterile. Permanent sterilization methods include but are not limited to hysterectomy, bilateral salpingectomy and bilateral oophorectomy. A postmenopausal state is defined as no menses for 12 months without an alternative medical cause. A high follicle stimulating hormone (FSH) level in the postmenopausal range may be used to confirm a postmenopausal state in women not using hormonal contraception or hormonal replacement therapy.

12. Women of childbearing potential and fertile men must agree to use adequate contraception when sexually active from signing of the informed consent form for the full study until at least 6 months after the last study drug administration. Patients must agree to utilize 2 reliable and acceptable methods of contraception simultaneously. A man is considered fertile after puberty unless permanently sterile by bilateral orchectomy. Men being treated with PCLX-001 are advised not to father a child during and up to 6 months after treatment; prior to treatment, advice should be sought for conserving sperm due to the chance of irreversible infertility as a consequence of treatment with PCLX-001. Female partners of childbearing potential from male study participants have to use adequate contraception / birth control between signing of the informed consent and 6 months after the last administration of the study drug if the male study participant is not sterilized.

The investigator or a designated associate is requested to advise the patient how to achieve highly effective birth control. Highly effective (failure rate of less than 1% per year) contraception methods, when used consistently and correctly, include:

- Combined (estrogen and progestin containing: oral, intravaginal transdermal and progestin-only (oral, injectable, implantable) hormonal contraception associated with inhibition of ovulation).
- Intra-uterine device (IUD) or intrauterine hormone-releasing system (IUS).
- Bilateral tubal occlusion or vasectomized partner (provided that partner is the sole sexual partner and has received medical assessment of the surgical success).
- Sexual abstinence (reliability to be evaluated in relation to the duration of the clinical trial and the preferred and usual lifestyle of the patient).

Male patients with a female partner of reproductive potential must use a condom and ensure that an additional form of contraception is also used during treatment and until 6 months after last study drug administration. Patients must agree to utilize reliable and acceptable methods of contraception simultaneously.

